Secondary Hypothesis 3B: Prehospital tranexamic acid as compared to placebo will attenuate trauma-induced pro-inflammatory changes and immunosuppression by reducing the early inflammatory cytokine response (GM-CSF, IFN- γ , IL-1 β , IL-2, IL-4, IL-5, IL-6, IL-8, IL-10 and TNF- α), HMGB1 levels and early inflammatory gene responses as measured by RT-PCR.

E.3.4. Secondary Aim#4: Determine whether different dosing regimens of tranexamic acid upon arrival in the hospital are associated with improvements in hyperfibrinolysis, markers of coagulopathy, clinical outcomes, platelet and leukocyte activation and the early inflammatory response.

Secondary Hypothesis 4A: Repeat dosing of 1 gram of tranexamic acid followed by 1 gram over approximately 8 hours after hospital arrival in patients who have already received 1 gram of prehospital tranexamic acid will lower the incidence of 12 hour (from arrival) hyperfibrinolysis (estimated percent lysis > 7.5%), coagulopathy (INR > 1.4) and improve r-TEG markers of coagulopathy, D-dimer levels, activated protein C levels and plasmin-antiplasmin complex levels as compared to standard dosing of tranexamic acid (1 gram over approximately 8 hours) or abbreviated dosing (no additional tranexamic acid).

Secondary Hypothesis 4B: Repeat dosing of 1 gram of tranexamic acid followed by 1 gram over approximately 8 hours after hospital arrival in patients who already received prehospital tranexamic acid will lower the incidence of 24 hour and 30 day mortality, acute lung injury, multiple organ failure and nosocomial infection as compared to standard dosing or abbreviated dosing.

Secondary Hypothesis 4C: Repeat dosing of 1 gram of tranexamic acid followed by 1 gram over approximately 8 hours after hospital arrival in patients who already received prehospital tranexamic acid will reduce 12 hour (from arrival) base deficit, 24 hour crystalloid requirements and 6 hour and 24 hour blood and blood component transfusion requirements (PRBC, FFP and platelets) as compared to standard dosing or abbreviated dosing.

Secondary Hypothesis 4D: Repeat dosing of 1 gram of tranexamic acid followed by 1 gram over approximately 8 hours after hospital arrival in patients who already received prehospital tranexamic acid will reduce 12 hour and 24 hour (from arrival) markers for platelet and leukocyte activation, plasmin

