I.2 Secondary Clinical Outcomes: Secondary clinical outcomes will include the incidence of hyperfibrinolysis (EPL > 7.5% by rapid-TEG analysis) upon arrival to the trauma bay within the first 6 hours, the incidence of acute traumatic coagulopathy (INR > 1.4), 24 hour mortality, acute lung injury, multiple organ failure, the development of nosocomial infection, early (24hr) seizures, in-hospital pulmonary embolism, presenting base deficit, 24 hour crystalloid requirements and 6 hour and 24 hour blood and blood component transfusion requirements (PRBC, FFP and platelets). *These same clinical outcomes will similarly be used for the randomized tranexamic acid dosage regimen comparison.*

I.3. Secondary Laboratory/Mechanistic Outcomes: All laboratory/mechanistic outcomes will be measured during the first 6 hours from trauma center arrival and at 12 and 24 hours (+/- 12 hours) out from injury. Those laboratory/mechanistic outcomes including flow cytometry which require fresh blood samples will be performed only at the University of Pittsburgh on a subset of patient samples unless participating centers have specific capabilities and following appropriate training for standardization. *These same laboratory/mechanistic outcomes will similarly be used for the randomized tranexamic acid dosage regimen comparison at 12 and 24 hours post-injury.*

I.4. Clinical Outcomes Methods/Definitions: All clinical outcomes will be prospectively evaluated for throughout ICU and hospital admission and the timing from the day of initial injury will be recorded for time-to-event statistical analysis.

I.4.1. 30 day and 24 hour mortality: 30 day mortality will be prospectively recorded from the day of trauma bay arrival. Over the first 24 hours we will document and record the time of death in hours. We suspect that patients enrolled will have a significant percentage of mortality that occurs in the first 24hrs.

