I.5. Laboratory/Mechanistic Outcome Methods/Definitions: All measurements will be performed within 6 hours of arrival and at 12 and 24 hours post injury (+/- 12 hours) for the randomized dosage regimen comparison. One more additional blood sample will be collected at 72 hours (\pm 12 hrs) for D-dimer, activated Protein C levels and plasmin-antiplasmin complexes measurements. Excluding r-TEG analysis and PT/ INR measurements, all blood and serum samples will be spun, stored and batched at their respective institution and delivered to the University of Pittsburgh where formal ELISA immunoassay measurements will be undertaken. Those laboratory/mechanistic outcomes including flow cytometry which require fresh blood samples will be performed only at the University of Pittsburgh on a subset of patient samples unless participating centers have specific capabilities and following appropriate training for standardization.

I.5.1. Coagulopathy and TEG parameters (Aim#2): To appropriately characterize differences in coagulopathy between tranexamic acid and placebo, in addition to r-TEG measurements of hyperfibrinolysis, presenting PT/ INR and additional TEG parameters will also be measured (ACT, r-value, k-time, α -angle, maximal amplitude, and G-values). All rapid TEG measurements will be performed within 6 hours of arrival and at 12 and 24 (+/- 12 hours) hours post injury. TEG analysis will be performed on a TEG[®] 5000 Thromboelastograph[®] Hemostasis Analyzer which will reside within the emergency department of each participating site. Standard laboratory INR will be drawn and measured at each institution within 6 hours of arrival and at 12 and 24 hours (+/- 12 hours). To further quantify the coagulopathy and hyperfibrinolysis post injury in these patients, D-dimer, activated Protein C levels and plasmin-antiplasmin complexes will be measured by ELISA plate assay. (ANIARA, USCN Life Science Inc., DRG International, Inc.) Plasmin-antiplasmin complexes may represent a more common, subclinical measurement of fibrinolytic activity that is not able to be assessed using standard TEG analysis, but elevated levels are associated with significantly worse outcome post injury and may be a marker than demonstrates the mechanism by which tranexamic acids has it beneficial effects.

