The overarching goal of the study proposal is to assess the efficacy of prehospital tranexamic acid as compared to placebo for injured patients at risk for traumatic hemorrhage who require emergency medical transport. Additional goals include dose regimen comparison and characterization of the mechanisms responsible for tranexamic acid's beneficial effects. All primary and secondary analyses will be performed based on the Intent-to-Treat principle for the prehospital randomization and analyses will include all enrolled patients grouped by randomization assignment.

J.1. Data Analysis for Primary Outcome: We follow an intent-to-treat approach in analyzing our primary outcome of 30 day mortality.

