
J.2. Analysis of Prehospital Randomized Secondary Outcomes: Unless there is sufficient power (predetermined before the analysis is begun), the approach to analysis of secondary endpoints will generally be calculation of confidence limits on intervention group differences or model parameters rather than formal tests of significance at a specified critical level as the trial will not have sufficient power to detect difference in all of these outcomes. However, these comparisons will add to the knowledge of the benefits and risks of the interventions. Parametric and nonparametric comparisons will be applied according to normalcy. All tests used will be two-tailed tests at significance level (α) of 0.05. For prehospital randomized clinical outcomes we will use Chi-square with 95% confidence intervals for dichotomous outcomes and parametric or non-parametric testing for continuous variable with 95% confidence intervals. For prehospital randomized laboratory or exploratory outcomes we will use parametric or non-parametric testing for continuous variable with 95% confidence intervals.

J.3. Analysis for Second Stage In-hospital Randomized Dosage Regimens: Chi-square test will be able to test the effect of different tranexamic dosage regimens on hyperfibrinolysis. Similarly, chi-square will be used to detect any differences between dosage groups for 30 day mortality. To detect a trend in dosage response, test for trend will be implemented. As additional analysis and to account for site and to adjust for some important covariates, we will use logistic regression to test the effect of dosage on hyperfibrinolysis. Similarly Cox proportional hazards regression can be used for 30 day mortality. *For In-hospital randomized dosage regimen comparison for clinical outcomes* we will use Chi-square with 95% confidence intervals for dichotomous outcomes and parametric or non-parametric testing for continuous variable with 95% confidence intervals. *For In-hospital randomized dosage regimen comparison for laboratory or exploratory outcomes* we will use parametric or non-parametric testing for continuous variable with 95% confidence intervals.

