J.7. Missing Data: For 30-day mortality, given the transient nature of many of the subjects, extensive efforts will be made to ascertain vital status (see N.6.). Batch searches of the mortality databases will continue every quarter for subjects with unknown status, until trial closeout. For interim and final analyses, subjects who have not been reported as deceased by day 30 following ED admission from any of these sources we will use multiple imputation for the final value. As sensitivity analyses we will report the data with and without imputation. We will also report an analysis consistent with that used in other studies counting those missing as alive on day 30.

K. Sample Size Justification and Power Analysis:

We have determined the sample size for this proposal and powered the analysis based upon the primary outcome, 30 day mortality.

K.1. Primary Outcome 30 day mortality: Assuming a baseline mortality risk of 16% as was demonstrated in the Crash-2 study^{41,43} with 30 day mortality as the primary outcome, using a two-sided Z test with pooled variance and a 2 sided alpha of 0.05 the study will have a 90% power to detect a 7% or greater difference in 30

day mortality. The study will have 80% power to detect a 6% or greater difference in 30 day mortality. Using this power analysis, **497 patients in each arm, 994 total patients will be required, with a power of 0.85 and 2 sided alpha of 0.05. This will require on average each center to enroll 80 patients per year or 1 to 2 per week.** As busy, level 1 trauma centers with robust emergency medical programs were screened using the proposed inclusion criteria over 2012 data and selected for participation based upon this information, this sample size estimate is appropriate and attainable.

Power	Sample Size Grp 1 N1	Sample Size Grp 2 N2	Prop H1 Grp 1 or Trtmnt P1	Prop Grp 2 or Control P2	Diff if H0 D0	Diff if H1 D1	Target Alpha	Actual Alpha	Beta
0.9000	497	497	0.0919	0.1600	0.0000	-0.0681	0.0500		0.1000
0.8500	497	497	0.0965	0.1600	0.0000	-0.0635	0.0500		0.1500
0.8000	497	497	0.1003	0.1600	0.0000	-0.0597	0.0500		0.2000

L. Human Subjects:

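### The 12-hour regimen comparisons of hyperfibrinolysis and INR run only on patients alive at the draw, with no rule for earlier deaths, so a lysis benefit can be masked or its sign reversed

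*Combined protocol and SAP*

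**What the plan says.** Hypothesis 4A (section E.3.4) compares the three in-hospital regimens on the 12-hour markers and expects repeat dosing to do better: it "will lower the incidence of 12 hour (from arrival) hyperfibrinolysis (estimated percent lysis > 7.5%), coagulopathy (INR > 1.4"). Hypothesis 4B expects that repeat dosing "will lower the incidence of 24 hour and 30 day mortality, acute lung injury, multiple organ failure and nosocomial infection" relative to the same two comparators.

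For the analysis, section J.3 says "Chi-square test will be able to test the effect of different tranexamic dosage regimens on hyperfibrinolysis", adds logistic regression for hyperfibrinolysis, and names 30-day mortality for a regimen comparison as well. The only missing-data rule is section J.7, which opens "For 30-day mortality, given the transient nature of many of the subjects, extensive efforts will be made to ascertain vital status" and goes no further than that outcome. The opening of section J says "All primary and secondary analyses will be performed based on the Intent-to-Treat principle for the prehospital randomization". No equivalent sentence is given for the second-stage randomisation.

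On early death, section I.4.1 says "We suspect that patients enrolled will have a significant percentage of mortality that occurs in the first 24hrs" and provides for recording the hour of death over that period. On timing, section I.5.1 says "All rapid TEG measurements will be performed within 6 hours of arrival and at 12 and 24 (+/- 12 hours) hours post injury", whereas Hypothesis 4A counts its 12 hours from arrival.

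**The concern.** A patient who dies after second-stage allocation and before the draw has no EPL or INR value. Without a rule, that patient leaves both numerator and denominator, and the groups entering the chi-square are no longer the groups that were randomised.

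The protocol's own premises make this loss informative. Section C.2 attaches a 4-fold higher mortality risk to coagulopathy on admission. Section I.5.1 ties raised fibrinolytic activity to worse outcome. Hypothesis 4B expects 24-hour mortality to differ by regimen. If 4B is true, the better regimen keeps alive more of the patients most likely to be positive at 12 hours, and the survivor-only test of 4A is biased against it. Aim 4 is meant to guide the choice of dosing, and hyperfibrinolysis is the first endpoint J.3 names for that comparison.

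**Working it through.** The documents give no rate, sample size or power for the 12-hour endpoints, so there is no plan figure to reproduce. The inputs below are assumptions unless a source is named.

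**Inputs**
- h: share hyperfibrinolytic at arrival; 10%, with 5% and 15% as the range.
- d: death before the draw among them; 50% on one regimen and 25% on the other, with 40% v 30% as a milder case.
- o: death before the draw in everyone else; 3%.
- k: share of surviving hyperfibrinolytic patients still positive at 12 hours; 40% on both regimens. No one else is positive.
- Patients per regimen: 497 / 3 ≈ 166 (497 from section K.1; equal split assumed).

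**Formulas**
- Survivor-only incidence = h(1 − d)k / [1 − hd − (1 − h)o]
- Event or death before the sample = h(1 − d)k + hd + (1 − h)o

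**Base case, h = 10%**
- More early deaths (d = 50%): 0.020 / (1 − 0.050 − 0.027) = 0.020 / 0.923 = 2.2%. Composite: 0.020 + 0.077 = 9.7%.
- Fewer early deaths (d = 25%): 0.030 / (1 − 0.025 − 0.027) = 0.030 / 0.948 = 3.2%. Composite: 0.030 + 0.052 = 8.2%.

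| h | d | Survivor-only | Composite | Deaths as share of composite events |
|---|---|---|---|---|
| 10% | 50% v 25% | 2.2% v 3.2% | 9.7% v 8.2% | 79% v 63% |
| 5% | 50% v 25% | 1.1% v 1.6% | 6.4% v 5.6% | 84% v 73% |
| 15% | 50% v 25% | 3.3% v 4.8% | 13.1% v 10.8% | 77% v 58% |
| 10% | 40% v 30% | 2.6% v 3.0% | 9.1% v 8.5% | 74% v 67% |

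In each row the survivor-only figure favours the regimen with more deaths, and the composite favours the other.

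**How much true lysis benefit removes the reversal.** Set the two survivor-only figures equal and solve for k on the better regimen. Base case: 0.0217 × 0.948 / 0.075 = 0.27. Milder case: 0.0257 × 0.943 / 0.070 = 0.35. So a fall in persistence from 40% to about 27% (or about 35%) is hidden completely, a smaller fall appears with the wrong sign, and a larger one appears with the right sign but understated.

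**Chance of a significant wrong-way result.** At about 166 per regimen the base case is 166 × 0.020 = 3.3 events against 166 × 0.030 = 5.0. A pairwise two-sided 5% test, by normal approximation (rough at such counts), is significant in the wrong direction about 8% of the time; across the four rows, about 4% to 10%.

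**Cross-check with a second model.** Let d0 and d1 be death before the draw on the comparator and on repeat dosing, r the comparator rate in survivors, RR the true effect in patients who would survive on either regimen, and q the rate in patients whom repeat dosing saves. Survivor-only rate on repeat dosing = [(1 − d0)·r·RR + (d0 − d1)·q] / (1 − d1).
- d0 = 8%, d1 = 4%, r = 5%, q = 0.5, RR = 1: (0.046 + 0.020) / 0.96 = 6.9% against 5.0%.
- The same with RR = 0.7: (0.0322 + 0.020) / 0.96 = 5.4% against 5.0%, still reversed.
- Over d0 of 4–10%, d1 of 2–5%, r of 5–20% and q of 30–100%, with RR = 1, repeat dosing looks worse in all 45 combinations. The chance of a significant wrong-way result runs from about 3% to 48%; the top value needs d0 = 8%, d1 = 2%, r = 5% and q = 1.
- With RR = 0.7 the sign never reverses at r = 20%.

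**The case against.** A reader might infer that a life-saving regimen would be judged inferior. The documents do not support that. No rule declares a regimen inferior, this is a secondary aim, and J.3 and Hypothesis 4B put mortality beside the lysis result, where a conflict would be visible. In the four tabulated cases a significant wrong-way result is unlikely. All of this stands. It does not correct the marker comparison itself.

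A reader might also see a breach of the plan's own intent-to-treat statement, because section J says "analyses will include all enrolled patients grouped by randomization assignment". That sentence is limited to the prehospital randomisation. It does not clearly govern the regimen comparison, so the fair reading is a missing rule, not a contradiction.

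The reversal in the table assumes no regimen effect on lysis in survivors, whereas Hypothesis 4A posits one; the break-even figures above show how much that matters. The assumed death rates are also high. Every regimen patient received prehospital tranexamic acid, and section K.1 plans 9.2% to 10.0% 30-day mortality in that arm. The base case has 7.7% dead before the draw on its worse regimen. The 15% row has 10.05%, above that planned total, though one regimen may exceed the arm average.

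The link between lysis and death in the visible text is partly indirect, since it concerns fibrinolytic activity that standard TEG does not detect. The admission-coagulopathy figure in C.2 bears more directly on the INR endpoint.

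A patient dying at 5 hours might have a qualifying sample if the plus or minus 12 hours applies to the 12-hour draw. That is a reason to settle the window, because at present it is unclear who counts as dead before the sample.

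Finally, deaths make up 58% to 84% of composite events in the table, so the composite partly repeats the mortality comparison. That argues for adding it, not for substituting it.

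**Conclusion.** The concern holds in a limited form. As written, the 12-hour comparisons of EPL > 7.5% and INR > 1.4 between regimens condition on survival after randomisation, and no rule covers deaths before the draw. If a regimen prevents early deaths in hyperfibrinolytic patients, its lysis benefit can be understated, hidden or reversed in sign.

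The size rests on assumed rates. It requires that the patients saved are more often positive than other survivors, and that any true effect on lysis is modest. A masked benefit or reversed sign is the realistic risk; a significant wrong-way finding stayed below 50% in every scenario tried and at about 4% to 10% in the tabulated ones. The primary outcome is unaffected. The change is worth making before unblinding, since otherwise the handling of these deaths will be chosen with the data in view.

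**What to change.** In section J.3, for each dichotomous 12-hour endpoint:
- report by regimen the number of deaths before the draw;
- analyse event or death before the sample over all patients randomised to a regimen, beside the survivor-only comparison;
- state that the survivor-only result is conditional on survival and is not by itself a basis for ranking regimens.

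A worst-rank analysis of the continuous 12- and 24-hour markers, with death before the sample ranked worst, is an optional sensitivity analysis.

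Reconcile the time origin of the 12-hour sample (arrival in Hypothesis 4A, injury in sections I.3, I.5 and I.5.1) and state how its window of plus or minus 12 hours applies, so that death before the sample is defined.

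The cost is analysis-plan wording. Hour of death over the first 24 hours is already collected, so no new data, visits or patients are needed. The drawback is that deaths dominate the composite and deaths not due to bleeding add noise. It should therefore supplement the laboratory comparison and not replace it.
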